Appendix B. Schedule of Assessments – Long-Term Follow-Up

Assessments ^a	Weeks 28, 36, 44, 52	Week 32, 40	48	Weeks 56, 64, 80, 88	Week 72	Weeks 96	Early Term & 30-Day Follow-Up ¹
Clinical Assessments							
Physical Examination	X	X	X ^b	X	X	X	X
Child Pugh Score ^b			X			X	X
Vital Signs ^c	X	X	X	X	X	X	X
Weight ^d	X	X	X	X	X	X	X
Hip and Waist Circumference ^d	X	X	X	X	X	X	X
12-lead ECG			X			X	X
FibroScan ^{®e}			X			X	
MRI-PDFF						X ^m	X ^o
DXA			X ^p			X	
Liver Biopsy						X ^m	X ^o
CLDQ-NASH ^f	X		X			X	
Lifestyle Guidance ^g	X	X	X	X	X	X	
Administer Study Drug ^h	X	X	X	X	X	X	
Concomitant Medications	X	X	X	X	X	X	X
Adverse Events	X	X	X	X	X	X	X
Laboratory Assessments							
Chemistry, Hematology, Lipids, Coagulation ⁱ	X	X	X	X	X	X	X
Serum & Plasma Storage Samples ^j	X	X	X	X	X	X	X

[figure not shown]
Assessments ^a	Weeks 28, 36, 44, 52	Week 32, 40	48	Weeks 56, 64, 80, 88	Week 72	Weeks 96	Early Term & 30-Day Follow-Up ¹
Fibrosis Biomarkers ⁱ			X		X	X	X
Other Biomarkers ⁱ		X	X		X	X	X
PK		X	X	X	X	X	X
ADA and NAB ⁿ		X	X	X	X	X	X
Endogenous FGF21		X	X	X	X	X	X
Pregnancy testing ^k	X	X	X	X	X	X	X

ADA = anti-drug antibodies; BP = blood pressure; ECG = electrocardiogram; HR = heart rate; PE = Physical Examination; PK = pharmacokinetic; NAB = neutralizing antibody

- a In-clinic visits will be conducted every 4 weeks \pm 5 days from Week 28 to Week 56 and then every 8 weeks \pm 7 days from Week 64 to Week 96.
- b Complete PE including assessment at Week 48, otherwise symptom-driven. Child-Pugh (CP) Score assessments should be completed as part of the physical exam at Week 48, Week 96, and ET & 30-Day Follow-up.
- c Vitals to include systolic and diastolic BP, pulse, respiration rate will be collected at each visit. Triplicate blood pressure (to be measured in same arm with at least two minutes rest between BP measurements) and heart rate to be collected at Week 48 and Week 96. Single measurements to be collected at all other visits.
- d Weight, waist and hip circumference should be obtained by the same study personnel as much as possible across visits for each subject to minimize variability in the measurement. On dosing days, weight will be collected pre-dose. Weight should be obtained using a calibrated scale. The subject should be weighed in consistent clothing.
- e At least 2-3 hours fasting is required prior to all elastography assessments.
- f If the CLDQ-NASH is missed at Baseline/Day 1, questionnaire should not be collected at the remaining timepoints. It is recommended that the questionnaire be completed prior to any study procedures being performed and prior to the subject seeing a health care provider.
- g At each visit, subjects will be asked if there has been a significant change in diet, or physical activity.
- h Administration of study drug should occur following all other study procedures and sample collection for that visit. Beginning at Week 25, weekly administration of study drug is required either on site or utilizing in-home nursing for the following visits: Weeks 25-27, 29-31, 33-35, 37-39, 41-43, 45-47, 49-51, 53-55, 57-63, 65-71, 73-79, 81-87, and 89-95. Administration of last dose of study drug will occur at Week 95.
- i Refer to Table of Clinical Laboratory Assessments. Samples to be collected in the morning following an overnight fast of at least 8 or 12 hours where indicated.
- j Serum & plasma storage samples banked for possible additional clinical testing.
- k For female subjects of childbearing potential only. Urine pregnancy test at all time points.
- l Early Termination visit should occur within 5 days of discontinuation of study drug. The 30-Day Follow-Up visit should occur 30 days following the last dose of study drug received.
- m Additional biopsy required at Week 96. The liver biopsy should be obtained (-) 8 weeks to (+) 4 weeks from the scheduled visit date. MRI-PDFF to be obtained \pm 5 days from the liver biopsy.
- n Samples will be obtained for detection of ADA against EFX and if required a neutralizing ADA assay will be run on the same sample.

- o Liver Biopsy may be required for adjudication of pre-specified liver-related outcomes or to be obtained at Early Termination only if the previous liver biopsy was obtained \geq 12 months prior. MRI-PDFF to be performed if a liver biopsy is obtained, \pm 5 days from the liver biopsy.
- p DXA to be obtained \pm 10 days of the Week 48 Visit.

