3.3. Early Termination

If discontinuation of study drug occurs, the subject should return to the clinic within 5 days to perform the Early Termination (ET) assessments.

Subjects with ongoing clinically significant clinical or laboratory findings will be followed until the finding is resolved or medically stable; reasonable attempts will be made to follow up with subjects. The subject's participation will end once all study assessments and the 30-Day Follow-up visit has been completed.

The ET assessments are outlined in the Schedule of Assessments ([Appendix A - B](#)).

3.4. 30-Day Follow-up

The 30-Day Follow-up visit should be completed 30 days following the last dose of study drug received.

The 30-Day Follow-up assessments are outlined in the Schedule of Assessments ([Appendix A - B](#)).

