6.22. Adverse Events

An AE is any unfavorable and unintended sign (including an abnormal laboratory finding), symptom, or disease temporally associated with the use of a study drug, whether or not related to the study drug. AEs may also include pre- or post-treatment complications that occur as a result of protocol specified procedures, lack of efficacy, overdose, drug abuse/misuse reports, or occupational exposure. Pre-existing events that increase in severity or change in nature during or as a consequence of participation in the clinical study will also be considered AEs. AEs that occur after the first dose of EFX or during the study treatment and safety follow up periods will be documented on the AE eCRF. The Investigator will assess the AE severity and relationship of the AE to study drug. The Investigator will treat the subject as medically required.

Laboratory values that are outside the laboratory reference range of normal should be reported as AEs only if considered clinically significant by the Investigator.

From the time of obtaining informed consent until 30 days after the last administration of study drug, all SAEs and non-serious AEs related to protocol-mandated procedures will be recorded on the SAE/AE eCRF. All other untoward medical occurrences observed during screening, including exacerbation or changes in medical history, will be captured on the medical history eCRF. Details on recording and reporting AEs are provided below.

Clinical judgment of the Investigator should be used to determine whether a subject is to be withdrawn due to an AE. In the event the subject requests to withdraw from study-related

treatment or the study due to an AE, the subject should be followed for the safety follow up period as outlined in the Schedule of Assessments.

All subjects experiencing AEs, including clinically significant abnormal laboratory values, whether or not associated with use of the study drug, must be monitored until the condition returns to normal, returns to the subject's baseline, until the Investigator determines the AE has reached a stable outcome and is no longer clinically significant, or the subject is considered lost to follow up.

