6.22.6. Reporting Adverse Events

6.22.6.1. Reporting Procedures for Non-Serious Adverse Events

The Investigator is responsible for ensuring that all AEs observed by the Investigator or designee or reported by the subject are reported using the AE eCRF.

The Investigator will assign the following AE attributes:

- AE diagnosis or syndrome(s), if known (if not known, signs or symptoms)
- Dates of onset and resolution (if resolved)
- Severity
- Relatedness to study drug or study-related procedures
- Action taken with study treatment

Follow-up of non-serious AEs will continue through the last day on the study participation and/or until a definitive outcome (e.g., resolved, resolved with sequelae, lost to follow-up) is achieved.

When a subject is withdrawn from the study because of a non-serious AE, the Sponsor and/or designee must be notified by e-mail or phone within 48 hours.

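### A Week 96 biopsy taken on Days 697–701 falls after the procedure-AE recording rule, the 30-Day visit and the TEAE summaries have ended, a minor gap in capturing non-serious complications

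*Protocol*

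**What the plan says.** **Biopsy and last dose.** Footnote m of protocol Appendix B requires a further biopsy at Week 96 and gives its window: "The liver biopsy should be obtained (-) 8 weeks to (+) 4 weeks from the scheduled visit date". Footnote h says "Administration of last dose of study drug will occur at Week 95". The dosing row of the same table, "Administer Study Drug ^h", is nevertheless marked at Week 96.

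**What ends 30 days after the last dose.**
- The specific recording rule in protocol 6.22, repeated in SAP 3.5: "until 30 days after the last administration of study drug, all SAEs and non-serious AEs related to protocol-mandated procedures will be recorded".
- The last scheduled visit, Appendix B footnote l: "The 30-Day Follow-Up visit should occur 30 days following the last dose of study drug received". It is tied to the dose, not to the biopsy.
- The TEAE definition (protocol 7.8.2, SAP 7.7.2) and the safety summaries (protocol 7.8, SAP 7.7). The SAP's overview and its SOC/PT tables for procedure-related events are restricted to TEAEs.

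**What is wider.**
- A general sentence in 6.22 has no stated end day: "AEs that occur after the first dose of EFX or during the study treatment and safety follow up periods will be documented".
- Section 6.22.6.1 makes the investigator responsible for every AE observed or reported, and says "Follow-up of non-serious AEs will continue through the last day on the study participation".
- Section 3.3, written for early termination, says "participation will end once all study assessments and the 30-Day Follow-up visit has been completed".
- Section 6.22.6.2 keeps related SAEs reportable after the window.
- All AEs collected go into listings (protocol 7.8.2, SAP 7.7.2).

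**The concern.** The biopsy is invasive and required by the protocol, so the rules for recording its complications should outlast it. Here the biopsy window is tied to the Week 96 visit while the safety rules are tied to the last dose, one week earlier. At the late end of the window the biopsy can follow the close of the recording rule, the last scheduled contact and the summary period. A non-serious complication, for example pain or minor bleeding, may then go unrecorded. If it is recorded, it still cannot enter the table of procedure-related TEAEs. The Week 24 biopsy has no such problem in subjects who stay on treatment, because dosing and visits continue past it.

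**Working it through.** **Inputs.** SAP 6.1 counts Day 1 as the first dose and numbers later days as date difference plus 1, so a nominal visit at week w is Day 7w + 1. Last dose at Week 95 (footnote h). Biopsy window −8 to +4 weeks (footnote m). Recording rule, 30-Day visit and TEAE cut at last dose + 30 days.

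**Reproducing the plan's own figure.** Week 96: 7 × 96 + 1 = Day 673, the SAP's target day for Week 96 histology. Weeks 24 and 48 give Days 169 and 337, also as in the SAP.

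**Dates.**
- Last dose: 7 × 95 + 1 = Day 666.
- End of the recording rule, 30-Day visit and TEAE period: 666 + 30 = Day 696.
- Biopsy window: 673 − 56 = Day 617 to 673 + 28 = Day 701, which is 701 − 617 + 1 = 85 days.
- Latest biopsy: 701 − 666 = 35 days after the last dose and 701 − 696 = 5 days past the cutoff.
- Window days past the cutoff: Days 697–701, 5 of 85 = 5.9%.

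**Size under different timings.** The documents do not say how biopsies will be spread, so these are assumptions.
- All done by the Week 96 visit: 0%. Each then has at least 696 − 673 = 23 days before the cutoff.
- Evenly spread over the window: 5.9%. With 40 subjects per arm (protocol 5.2.2) and no dropout, that is at most 0.059 × 40 = 2.4 per arm, or about 7 of 120.
- All spread over the 28 days after the visit: 5/28 = 18%. The window itself leans early: 57 of its 85 days are at or before the visit.

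**Sensitivity of the cutoff.**
- If the dosing row were right and the last dose fell at Week 96, the cutoff would be 673 + 30 = Day 703, and the latest nominal biopsy would be 2 days inside it.
- If the biopsy window were counted from the actual visit (±7 days, footnote a) with the last dose still on Day 666, the latest biopsy would lie between Day 694 and Day 708: from 2 days before to 12 days after the cutoff.

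**Does the wider text close the gap?** The general sentence in 6.22 refers to the safety follow-up period, but the only scheduled visit in that period is the 30-Day visit. Applying section 3.3, a late biopsy would keep the subject in the study until the biopsy or its MRI, which footnote m allows up to 5 days later. No AE contact is scheduled after that. The SAE rule covers serious related events only. A site may therefore record a later non-serious event, but no visit or call prompts it, and an event starting after Day 696 is not a TEAE.

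**The case against.** The strongest reply is that recording does not really stop on Day 696. The general sentence in 6.22 is open-ended. The 30-day sentence can be read as mainly limiting what is recorded before dosing, since the next sentence deals with other occurrences during screening. Section 6.22.6.1 covers all AEs observed or reported. Section 6.8 recommends observation after a biopsy to the institution's standard of care, so early complications would often be seen by staff. Section 6.16 brings ADA-positive subjects back for sampling. Much of this stands, and a reader who inferred that all AE recording ends on Day 696 would go too far. It narrows the loss to non-serious complications that appear after the subject leaves and are not volunteered. The ADA visits are for sampling and do not cover placebo.

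A second reply concerns the table. A reader might infer that the procedure-related TEAE table would understate biopsy risk because of this gap. The documents do not support resting the case on that: SAP 7.7.2 classes events before the first dose as pre-treatment, so screening-biopsy complications are already outside it. The table is not a full measure of biopsy risk, and a treatment-anchored TEAE window is a legitimate choice.

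A third reply is that the gap vanishes if a dose is given at Week 96, as the dosing row suggests. Footnote h is explicit and its list of weekly dosing ends at Week 95, so Week 95 is the better-supported reading. Even so, the two instructions conflict, and which one a site follows decides whether an event falls inside the cutoff.

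**Conclusion.** The point holds as a minor safety-capture gap. With the last dose at Week 95 and nominal dates, biopsies on Days 697–701 fall outside the specific recording rule, the final visit and the TEAE summaries. That is 5 of 85 window days: about 6% of biopsies if evenly spread, none if all are done by the visit. Only non-serious events are exposed. Related SAEs remain reportable and collected AEs are listed.

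Two stronger readings do not follow. One is that biopsies in the days just before Day 696 are also under-covered. That needs a post-biopsy observation period, and the documents give none; for those biopsies the 30-Day visit still falls on or after the biopsy day. The other is that time off drug at a late biopsy or MRI weakens the efficacy results. The documents give nothing from which such an effect could be estimated. The AE-recording gap does not touch the efficacy analyses, and the primary endpoint is at Week 24.

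**What to change.** 1. Remove the Week 96 mark from the dosing row of Appendix B so that it agrees with footnote h.
2. In protocol 6.22 and footnote m, record procedure-related AEs until the later of last dose + 30 days and a fixed period after the Week 96 biopsy, for example 7 to 14 days (a suggestion, not a figure from the documents). Add one telephone contact when that period runs past Day 696. Align SAP 3.5, which repeats the rule.
3. In SAP 7.7.2, show any procedure-related AE starting after last dose + 30 days on a separate line beside the procedure-related TEAE summary. Leave the TEAE definition unchanged.

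The biopsy window and all efficacy analyses stay as they are. The cost is one table correction, one recording rule, one call for subjects with late biopsies and one extra table line. For the latest biopsy, recording would end on Day 708 (701 + 7) or Day 715 (701 + 14), 12 or 19 days past Day 696.

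SAP section 8 describes dosing to Week 96 in the past tense, so the biopsies may already be complete. If they are, only item 3 applies, to whatever was collected.

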Appendix C

Appendix D Pregnancy Precautions, Definition for Female of Childbearing Potential, and Contraceptive Requirements

1) Definitions

a) Definition of Childbearing Potential

For the purposes of this study, a female born subject is considered of childbearing potential following the initiation of puberty (Tanner stage 2) until becoming post-menopausal, unless permanently sterile or with medically documented ovarian failure.

Women are considered to be in a postmenopausal state when they are \geq 54 years of age with cessation of previously occurring menses for \geq 12 months without an alternative cause. In addition, women of any age with amenorrhea of \geq 12 months may also be considered postmenopausal if their follicle stimulating hormone (FSH) level is in the postmenopausal range and they are not using hormonal contraception or hormonal replacement therapy.

Any testing (e.g., of FSH levels to confirm postmenopausal status) is not mandated by the protocol as a study procedure. It is the responsibility of the Investigator to confirm postmenopausal status.

Permanent sterilization includes hysterectomy, bilateral oophorectomy, or bilateral salpingectomy in a female subject of any age.

b) Definition of Male Fertility

For the purposes of this study, a male born subject is considered of fertile after the initiation of puberty unless permanently sterile by bilateral orchidectomy or medical documentation.

2) Contraception Requirements for Female Subjects

a) Study Drug Effects on Pregnancy and Hormonal Contraception

No formal studies have been conducted to evaluate the reproductive toxicity of EFX; therefore, the reproductive toxicity of EFX in humans is unknown.

EFX has not yet been studied in pregnant women.

Please refer to the latest version of the Investigator's Brochure for additional information.

b) Contraception Requirements for Female Subjects of Childbearing Potential

The inclusion of female subjects of childbearing potential requires the use of highly effective contraceptive measures. They must have a negative serum pregnancy test at screening and a negative pregnancy test on the Baseline/Day 1 visit prior to randomization. Pregnancy tests will be performed per Schedule of Assessments. Female subjects must agree to one of the following from screening until the 30-Day Follow-up Visit.

- Complete abstinence from intercourse of reproductive potential. Abstinence is an acceptable method of contraception only when it is in line with the subject's preferred and usual lifestyle.

Or

- Consistent and correct use of 1 of the following methods of birth control listed below.

 - Intrauterine device (IUD) with a failure rate of < 1% per year
 - Intrauterine hormone-releasing system (IUS) with a failure rate of < 1% per year
 - Tubal sterilization
 - Essure® micro-insert system (provided confirmation of success 3 months after procedure)
 - Vasectomy in the male partner (provided that the partner is the sole sexual partner and had confirmation of surgical success 3 months after procedure)

Should female subjects wish to use a hormonally based method, use of a male condom by the female subject's male partner is required. Subjects who utilize a hormonal contraceptive as one of their birth control methods must have used the same method for at least three months prior to study dosing. Hormonally-based contraceptives permitted for use in this protocol are as follows:

- Oral contraceptives (either combined or progesterone only)
- Injectable progesterone
- Implants of levonorgestrel
- Transdermal contraceptive patch
- Contraceptive vaginal ring

Not all of these methods may be approved in each of the countries where the study is being conducted: please refer to local product information. Additional local regulatory requirements may apply.

Female subjects must also refrain from egg donation and in vitro fertilization during treatment and until at least 90 days after the last dose of study drug.

3) Contraception Requirements for Male Subjects

It is theoretically possible that a relevant systemic concentration may be achieved in a female partner from exposure of the male subject's seminal fluid. Therefore, male subjects with female partners of childbearing potential must use condoms during treatment until 90 days after the last

dose of study drug. Female partners of male study subjects are asked to select one of the above methods.

Male subjects must also refrain from sperm donation during treatment and until at least 90 days after the last dose of study drug.

4) Unacceptable Birth Control Methods

Birth control methods that are unacceptable include periodic abstinence (e.g., calendar, ovulation, symptothermal, post-ovulation methods), withdrawal (coitus interruptus), spermicides only, and lactational amenorrhea method (LAM). Female condom and male condom should not be used together.

5) Procedures to be Followed in the Event of Pregnancy

Subjects will be instructed to notify the Investigator if they become pregnant at any time during the study, or if they become pregnant within 90 days of last study drug dose. Subjects who become pregnant or who suspect that they are pregnant during the study must report the information to the Investigator and discontinue study drug immediately. Subjects whose partner has become pregnant or suspects she is pregnant during the study must report the information to the Investigator. Instructions for reporting pregnancy, partner pregnancy, and pregnancy outcome are outlined in [Section 6.22.6.2](#).

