1.5. Pharmacokinetic Results

In type-2-diabetics, following a single dose, the median time to reach C_{max} ranged from 2 to 5 days. Following SC dosing, mean EFX area under the drug concentration versus time curve (AUC) values increased 309-fold over the 100-fold dose range. The mean EFX $t_{1/2}$ for the SC cohorts was approximately 3.3 days. The mean $t_{1/2,z}$ was approximately 2.62 days after intravenous (IV) dosing. Overall, the PK of EFX demonstrated slightly supra-proportional exposure.

In type-2-diabetics, following multiple doses, EFX exhibited approximately dose proportional PK after Q2W or QW SC administration of 7 mg to 140 mg. The median T_{max} values ranged from 2 to 3.5 days for all cohorts. EFX C_{max} and AUC increased dose-proportionally from 7 mg to 140 mg after Q2W or QW SC administration. Minimal accumulation was observed following Q2W dosing. Following QW dosing, moderate accumulation was observed, with mean accumulation ratios ranging from 1.56 to 3.61. No trend between dose and accumulation ratio was observed.

In NASH subjects, EFX exhibited approximately dose-proportional PK after QW administration of 28 to 70 mg; noncompartmental parameters for NASH subjects were estimated by a population PK model. Relative to type-2-diabetics, NASH subjects exhibited approximately 4-fold lower clearance yielding a half-life of approximately 9 days and an accumulation ratio of approximately 4-fold. Due to the apparent decrease in clearance, C_{max} and AUC are similarly increased approximately 4-fold in NASH subjects relative to the type-2-diabetics.

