If a subject becomes pregnant during the study or within the safety follow up period defined in the protocol, the Investigator is to stop dosing with study drug(s) immediately and the subject should be withdrawn from the study treatment. Early termination procedures and safety follow-up should be implemented at that time.

A pregnancy is not considered to be an AE or SAE; however, it must be reported to Labcorp Clinical Safety within 24 hours of knowledge of the event. Labcorp Clinical Safety will then provide the Investigator/site the Exposure In Utero (EIU) form for completion. The Investigator/site must complete the EIU form and fax/email it back to Labcorp Clinical Safety.

If the female partner of a male subject becomes pregnant while the subject is receiving study drug or within the safety follow up period defined in the protocol, the Investigator should notify Labcorp Clinical Safety as described above.

The pregnancy should be followed until the outcome of the pregnancy, whenever possible. Once the outcome of the pregnancy is known, the follow-up EIU form should be completed and faxed/mailed to Labcorp Clinical Safety. If the outcome of the pregnancy meets the criteria for immediate classification as an SAE (i.e., postpartum complication, spontaneous abortion, stillbirth, neonatal death, or congenital anomaly), the Investigator should follow the procedures for reporting an SAE.

Safety Contact Information:

Labcorp Clinical Safety

Facsimile: United States [name] (Global fax numbers located in Study Binder)

E-mail: [contact]

Some SAEs will qualify for reporting to the Food and Drug Administration (FDA) as applicable via the MedWatch/CIOMS reporting system in accordance with FDA and other applicable regulations. The Sponsor or its designee will report SAEs and/or SUSARs as required to regulatory authorities and Investigators in compliance with all reporting requirements according to local regulations and Good Clinical Practice (GCP).

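### Female subjects may stop contraception 30 days after the last dose, about 3.3 half-lives, while four other limits in the same appendix run to 90 days

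*Protocol*

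**What the plan says.** The pregnancy-precautions appendix is labelled Appendix D in the body of the protocol and Appendix C in its list of appendices. Item 2b sets the end of contraception for women of childbearing potential: "Female subjects must agree to one of the following from screening until the 30-Day Follow-up Visit". Section 3.4 fixes that visit: "The 30-Day Follow-up visit should be completed 30 days following the last dose of study drug received". Inclusion criterion 11 only refers back to the appendix, and nothing else in the protocol extends the female limit.

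The same appendix uses 90 days after the last dose for four other items:

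- Egg donation and IVF (item 2b): female subjects must "refrain from egg donation and in vitro fertilization during treatment and until at least 90 days after the last dose of study drug".
- Condoms (item 3): "male subjects with female partners of childbearing potential must use condoms during treatment until 90 days after the last" dose. The stated reason is possible exposure of a female partner through seminal fluid.
- Sperm donation (item 3): "Male subjects must also refrain from sperm donation during treatment and until at least 90 days after the last dose of study drug".
- A subject's own pregnancy (item 5): the investigator is to be told of a pregnancy during the study, "or if they become pregnant within 90 days of last study drug dose".

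Ninety days is not universal: item 5 limits reporting of a partner's pregnancy to the study period.

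On pharmacokinetics, Section 1.5 says that "NASH subjects exhibited approximately 4-fold lower clearance yielding a half-life of approximately 9 days".

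On reporting, item 5 points to Section 6.22.6.2, which begins: "If a subject becomes pregnant during the study or within the safety follow up period defined in the protocol". That section gives no number of days.

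**The concern.** The limits are in the wrong order. A woman who has been dosed directly may stop contraception at day 30. A man on study must use condoms to day 90 to protect a partner whose only exposure would be through seminal fluid. A female subject at day 35 may conceive naturally, may not have IVF, and must report the pregnancy if it occurs.

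At stake is a conception in the weeks just after day 30, when some drug is still present, in a trial whose appendix calls human reproductive toxicity unknown. It would also fall inside the 90 days in which the subject is already asked to report a pregnancy.

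There is a linked gap in reporting. The subject is asked to notify to day 90, but Section 6.22.6.2 relies on a safety follow-up period that it does not quantify, and the nearest numeric safety window (Section 6.22) is 30 days. A site could conclude that a pregnancy at day 60 needs no exposure-in-utero form.

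**Working it through.** The documents state no washout target in half-lives, so there is no figure of the plan's own to reproduce. The check is direct arithmetic.

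**Inputs**

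- End of female contraception: 30 days after the last dose (Appendix D item 2b with Section 3.4).
- Comparison limit: 90 days after the last dose (Appendix D items 2b, 3 and 5).
- Half-life in NASH subjects: about 9 days (Section 1.5).
- Assumed range for the half-life: 7 to 11 days. This range is not in the documents.

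**Formulas**, assuming first-order decline from the end-of-treatment level:

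- Half-lives elapsed = days / half-life. At day 30: 30/9 = 3.33. At day 90: 90/9 = 10.
- Fraction remaining = 2^(−days/half-life).
- Day on which 1% remains = half-life × log2(100) = half-life × 6.64.
- Share of the post-day-30 area under the curve that falls in the next d days = 1 − 2^(−d/half-life).

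| | 7 days (assumed) | 9 days (Section 1.5) | 11 days (assumed) |
|---|---|---|---|
| Remaining at day 30 | 5.1% | 9.9% | 15.1% |
| Remaining at day 45 | 1.2% | 3.1% | 5.9% |
| Remaining at day 60 | 0.3% | 1.0% | 2.3% |
| Remaining at day 90 | 0.01% | 0.1% | 0.3% |
| Day on which 1% remains | 47 | 60 | 73 |
| Share of remaining exposure in days 30–45 | 77% | 69% | 61% |
| Share of remaining exposure in days 30–60 | 95% | 90% | 85% |

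**Which half-life applies.** Section 1.5 also reports about 3.3 days after subcutaneous dosing in type 2 diabetics, and Section 1.6 mentions up to 3.5 days. With those values 30 days would be 30/3.3 = 9.1 or 30/3.5 = 8.6 half-lives, with 0.2% or 0.3% remaining, and a 30-day limit would be ample. The NASH value is the one for the population enrolled here. The 3.3 half-lives computed above and the 3.3-day half-life in diabetics share digits only by coincidence.

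**Reading the result.** Drug is still present at day 30 and negligible by day 90. Most of the remaining exposure falls in the first 15 to 30 days after the current limit. Five half-lives would be 45 days, so the half-life by itself does not lead to 90; the case for that number is agreement with the other limits in the appendix.

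**The case against.** The strongest reply is that different limits for different acts are not an error. Gamete donation, condom use and notification are separate matters, and asking for notification beyond the contraception period adds surveillance rather than contradicting it. That is fair for notification and weakens the egg-donation and IVF comparison somewhat. It does not answer the condom comparison, where the appendix's own reason is exposure of a woman to drug, by a route far less direct than injection.

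A reason may also exist outside these documents: the appendix refers to the Investigator's Brochure and to local requirements, neither of which is available here. This stands as a limit on the finding, and a stated reason would be an acceptable answer.

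Third, 90 days does not follow from the half-life, and 45 or 60 days would remove most of the residual exposure. This is correct.

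Fourth, the consequence is small. Section 1.3 reports no teratogenicity in rats or rabbits and no embryofetal toxicity up to 30 mg/kg/dose. A pregnancy test is scheduled at early termination and 30-day follow-up, and pregnancies to day 90 are already to be notified. All this stands and keeps the point minor. The animal data do not explain the difference in limits, because they apply equally to the items set at 90 days.

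Fifth, under blinding with 1:1:1 allocation, a longer limit would also bind women on placebo, who have no exposure to avoid. That is a real cost.

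Finally, a site that reads item 5 together with Section 6.22.6.2 can infer 90 days for reporting. It can, but the section that governs the action should carry the number.

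**Conclusion.** The concern holds, as an inexpensive improvement rather than a serious defect. Female contraception ends at 3.3 half-lives with about 9.9% of the end-of-treatment level remaining (5.1% to 15.1% over the assumed 7 to 11 days), while the appendix sets 90 days for four related items and gives no reason for the difference. The residual exposure applies only to women of childbearing potential who received EFX. No harm is asserted, and no efficacy analysis is affected.

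The conclusion rests on the approximate 9-day half-life, which Section 1.5 attributes to a population PK model, on first-order decline, and on the absence of a rationale in the protocol. Confidence is medium, because the Investigator's Brochure or local requirements could supply one.

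**What to change.** 1. In Appendix D item 2b, end female contraception 90 days after the last dose instead of at the 30-Day Follow-up Visit. If the sponsor keeps 30 days, the appendix should say why directly dosed women have the shortest limit.
2. In Section 6.22.6.2, state that pregnancies up to 90 days after the last dose are reported, in line with item 5.
3. As a text correction only, make the sentence in item 2a about the absence of formal reproductive toxicity studies agree with the fertility and embryofetal studies in Section 1.3. Keep the statement that human reproductive toxicity is unknown. This correction does not support the longer period.

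The cost is wording in two places plus the item 2a correction, and a consent update. Participants bear up to 90 − 30 = 60 more days of contraception, including women on placebo while the blind holds. No visit, sample or pregnancy test is added, and the Schedules of Assessments do not change.
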